# AEs will be reported as follows (check the arrangement to be used for this protocol):

			4.4
I.	IN Satativ	Monitorina	Ontity:
1.	I U Jaietv		CIILILV.

- ☐ Study Principal Investigator is an LIP and provides safety oversight
  - Review of AEs and SAEs will be conducted in regularly occurring research team meetings that at scheduled at pre-determined frequency. The review and any follow-up action will be documented in meeting minutes.
- ☐ Safety Officer/Monitor is an LIP and provides safety oversight
  - Review of AEs and SAEs will be conducted at predetermined intervals in accordance with the Safety Monitoring Plan developed for this study
  - Safety officer/monitor may be independent or part of study team, as appropriate to risk and phase of study
- □ Data Safety Monitoring Board/Committee (DSMB/C)
  - Review of AEs and SAEs will be conducted in accordance with the DSMB Charter and Data Safety Monitoring Plan developed for this study

#### ii. To IRB:

Within 5 days of becoming aware of them, a properly delegated study team member will report to the IRB any AE that meets the definition of an unanticipated problem (UAP), which means the event is are unexpected, related to the research procedures, and caused harm or risk of harm.

SAEs that do not meet the criteria for prompt reporting will be tabulated on an aggregate reporting form for submission at the time of continuing review.

**Note**: If there is an independent safety monitor for the study (e.g., Safety Officer, DMC, or DSMB), aggregate reports do not need to be submitted at the time of continuing review. Instead, a summary report from the monitor should be submitted at the time of continuing review.

#### iii. To FDA:

A narrative or tabular summary showing the most frequent and most serious adverse events by body system will be provided by the Sponsor to the FDA with each annual report in compliance with 21 CFR 312.33(b)(1).

# g. Serious Adverse Event Reporting

The Site Principal Investigator will immediately report to the Sponsor any serious adverse event, whether or not considered study intervention related, including those listed in the protocol or investigator brochure, and will include the study team LIP's assessment of whether there is a reasonable possibility that the study intervention caused the event.

Study endpoints that are serious adverse events (e.g. all-cause mortality) will be reported in accordance with the protocol unless there is evidence suggesting a causal relationship between

[name]: 18-0242 Page 12 Version: 07/03/2019

the study intervention and the event (e.g., death from anaphylaxis). In that case, the Site Principal Investigator must immediately report the event to the Sponsor.

All SAEs will be followed until satisfactory resolution or until the study team's LIP deems the event to be chronic or the participant is stable.

Serious adverse events that are considered related (i.e., determined to be possibly, probably, or definitely related) to the investigational product by the Sponsor will be followed until the event resolves or stabilizes. Any SAE that occurs after treatment completion, and is considered by the Sponsor to be related to the investigational product, will be documented and reported as appropriate.

#### i. To FDA:

The Sponsor is responsible for notifying the Food and Drug Administration (FDA). Events meeting the following criteria will be submitted to the FDA as expedited IND Safety Reports according to the following guidance and timelines:

# 7 Calendar Day Telephone or Fax Report

The Sponsor will notify the appropriate review division at the FDA of any fatal or life-threatening adverse event that is unexpected and assessed by the Sponsor to be possibly related to the use of the investigational product. An unexpected adverse event is one that is not already described in the investigational product's Investigator Brochure. Such reports are to be telephoned or faxed to the appropriate review division at FDA and to the manufacturer of the investigational product within 7 calendar days of first learning of the event.

The report will be completed using Form FDA 3500A (Mandatory Reporting).

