# D. Description, Risks and Justification of Procedures and Data Collection Tools:

Potential Risks: Studies have examined the risk of using fluorescein for multiple purposes with no serious side effects [21]. The FDA has already approved the use of sodium fluorescein in adults and children for diagnostic angiography of the retina and it is also widely used as a contrast agent. The dose and route of administration being used in this study are consistent with the FDA approval for use of this drug in children.

The use of intravenous sodium fluorescein in gastrointestinal procedures has been reported to be extremely safe. Side effects from these studies include nausea/vomiting, injection site erythema, rash, and epigastric pain. Other investigators have examined the safety profile of intravenous fluorescein use in angiography. In these studies, reported potential side effects of sodium fluorescein administration include, urticaria, syncope, respiratory reactions, cardiac reactions, and hypersensitivity reactions. Multiple mechanisms have been suggested such as vasovagal phenomenon, histamine release via a nonallergic pathway, and sympathetic discharge related to anxiety as the pathogenetic basis of these side effects. The most common symptoms (>20%) reported in these studies include malaise, headache, dizziness, and nausea/vomiting [22-24].

A reported side effect of Fluorescein is yellowish skin for 6-12 hours after administration and yellow urine for 24-36 hours after administration. Fluorescein is systemically cleared by 48 to 72 hours after administration.

The package insert for Fluorescein describes "care must be taken to avoid extravasation during injection as the high pH of fluorescein solution can result in severe local tissue damage." To alleviate this risk, the medication will be given IV push over 10 seconds.

Confidentiality of Study Data: Data including enrollment, study drug orders, pre-operative and postoperative exams and adverse event reporting will remain identifiable. De- identification of this information is not possible as patient identifying information is necessary for continued

[name]: 18-0242 Page 7 Version: 07/03/2019

patient safety monitoring and follow-up while in the trial.

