#### iii. Expectedness:

A study team member, who is a Licensed Independent Provider (LIP) will be responsible for determining whether an AE is expected or unexpected.

An AE will be considered unexpected if the nature, severity, or frequency of the event is not consistent with the risk information previously described for the study intervention.

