# 15 Calendar Day Written Report

The Sponsor will notify the appropriate review division at the FDA, in a written IND Safety Report, of any serious, unexpected AE that is considered reasonably or possibly related to the use of the investigational product. An unexpected adverse event is one that is not already described in the investigational product's investigator brochure.

Written IND Safety reports will include an Analysis of Similar Events in accordance with regulation 21 CFR § 312.32. All safety reports previously filed by the Sponsor with the IND concerning similar events will be analyzed and the significance of the new report in light of the previous, similar reports commented on.

Written IND safety reports with Analysis of Similar Events will be submitted to the appropriate review division at the FDA, and the manufacturer of the investigational product within 15 calendar days of first learning of the event, using Form FDA 3500A.

Written IND Safety Reports will be submitted to the IRB(s) of record in accordance with IRB Guidelines.

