## 2. Unanticipated Problems

## a. Definition of Unanticipated Problems (UAP)

An unanticipated problem involving risk to participants or others includes any incident, experience, or outcome that meets **all** of the following criteria:

- Unexpected in terms of nature, severity, or frequency given (a) the research procedures
  that are described in the protocol-related documents, such as the Institutional Review
  Board (IRB)-approved research protocol and informed consent document; and (b) the
  characteristics of the participant population being studied;
- Related or possibly related to participation in the research ("possibly related" means there is a reasonable possibility that the incident, experience, or outcome may have been caused by the procedures involved in the research); and
- Suggests that the research places participants or others at a greater risk of harm (including physical, psychological, economic, or social harm) than was previously known or recognized.

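### The 7- and 15-day FDA report rules define an unexpected event without the severity and frequency test that the protocol uses elsewhere, so a severe form of a listed reaction need not be expedited

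*Combined protocol and SAP*

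**What the plan says.** The protocol defines an unexpected event in several places.

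- **Section IV.G.1.d.iii (Expectedness)** gives the general rule, applied by a licensed practitioner on the study team: "An AE will be considered unexpected if the nature, severity, or frequency of the event is not consistent with the risk information previously described".
- **Section IV.G.1.g, 7 Calendar Day Telephone or Fax Report**: "An unexpected adverse event is one that is not already described in the investigational product's Investigator Brochure". The trigger is "any fatal or life-threatening adverse event that is unexpected and assessed by the Sponsor to be possibly related" to the product.
- **Section IV.G.1.g, 15 Calendar Day Written Report**: "An unexpected adverse event is one that is not already described in the investigational product's investigator brochure". The trigger is a serious, unexpected event judged reasonably or possibly related.
- **Section IV.G.2.a (Definition of Unanticipated Problems)** returns to nature, severity or frequency, but it governs reports to the IRB.

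The FDA subsection of IV.G.1.g makes the 7- and 15-day wording operative: "Events meeting the following criteria will be submitted to the FDA as expedited IND Safety Reports".

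Section IV.D (Potential Risks) says that studies of the dye showed no serious side effects. It then names, from angiography, "urticaria, syncope, respiratory reactions, cardiac reactions, and hypersensitivity reactions", with no grade or rate for any of them.

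**The concern.** An event has to be unexpected to trigger either expedited report, so the definition decides what the FDA hears about quickly. The general rule asks whether the event is worse or more frequent than the described risk. The two FDA rules ask only whether it is already described. For a reaction that is known as a class but has not been described in severe form, the two questions can give opposite answers.

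This matters for the present drug because its described risks are mostly of that kind. The reports cited in section IV.D for side effects include three whose titles concern anaphylaxis, one of them during intracranial surgery. The risk text itself names only the class, hypersensitivity reactions. A severe form is therefore foreseeable, and it is the case in which the definitions diverge. At stake is prompt notice to the FDA and the manufacturer of a severe dye reaction in a child.

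**Working it through.** No arithmetic underlies the rules themselves, so the check sets the texts side by side and then runs an example through each.

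**Step 1. Compare the definitions.**

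| Section | Governs | Test for unexpected | Measured against |
|---|---|---|---|
| IV.G.1.d.iii Expectedness | Assessment of every AE | Nature, severity or frequency | Risk information already described (no document named) |
| IV.G.1.g 7-day | FDA and manufacturer | Not already described | Investigator Brochure |
| IV.G.1.g 15-day | FDA and manufacturer, with a copy to the IRB | Not already described | Investigator Brochure |
| IV.G.2.a Unanticipated problems | IRB | Nature, severity or frequency | Protocol-related documents and study population |

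The FDA rules differ from the general rule in both the test and the reference document.

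**Step 2. Look for text that restores the wider test on the FDA route.** There is none. 21 CFR 312.32 is cited in the definition of an adverse event and, in the 15-day rule, for the analysis of similar events. Neither citation brings in a definition of unexpected. The serious adverse event section sends a drug-caused death to the Sponsor at once but adds no FDA trigger.

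**Step 3. Run an example: a fatal cardiac reaction, judged possibly related.** Assume the brochure uses the same broad terms as section IV.D.

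- Expectedness section: a death is not consistent in severity with risk information that reports no serious side effects. The event is unexpected.
- 7-day rule: fatal, yes; possibly related, yes; unexpected, no if read literally, because cardiac reactions are already described. The report is not required.
- 15-day rule: serious, yes; possibly related, yes; unexpected, no for the same reason. The report is not required.

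A cluster of serious cases of a listed reaction, at a rate above that described, behaves in the same way. It is unexpected by frequency under the general rule and already described under the 15-day rule.

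**Step 4. Count the reactions exposed.** Of the five reactions in the section IV.D sentence, three (respiratory, cardiac, hypersensitivity) are classes wide enough to run from trivial to fatal.

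**Step 5. Time to FDA notice if the event is not expedited.** The remaining route is the summary in the annual report, due within 60 days of the IND anniversary. For an event at the start of an IND year the longest wait is 12 months + 60 days, or about 14 months, against 7 or 15 calendar days.

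**Step 6. Check who is told in any case.** Section IV.G.1.g sends every serious event to the Sponsor immediately, whether or not related. Section IV.H sends all serious events to the DSMC within 5 business days, with no expectedness filter. An unanticipated problem goes to the IRB within 5 days, under a definition that keeps severity and frequency.

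**The case against.** The strongest reply is that the texts can be reconciled. The FDA rules say described, not listed. The Expectedness section is the general rule, so the FDA rules may only be naming the document that holds the description. On that reading a bare mention of cardiac reactions does not describe a cardiac death, and against a text that reports no serious side effects a death is plainly new. This reading is available, and the brochure cannot be checked. It follows that such an event need not be expedited, not that it will not be. The reply does not remove the conflict: the FDA rules give their own complete definition and do not refer back to the general one.

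A reader might also infer that a severe reaction could go unnoticed for a year. The documents do not support that. The Sponsor and the DSMC, which can suspend or close the trial, hear within days, and the DSMC must approve the move to the second phase.

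Two further inferences are tempting and do not hold.

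- The IRB reporting paragraph describes an unanticipated problem as "unexpected, related to the research procedures, and caused harm or risk of harm", whereas the definition says "Related or possibly related to participation in the research". This could look like a narrower causality threshold. But the paragraph applies to events that meet the definition, so it takes in the wider wording.
- The causality scale heads one category Potentially Related, while the reporting rules say possibly. The same entry in the scale uses possibly related in its own text, so the terms are equated.

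Both are matters of copy-editing.

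**Conclusion.** The inconsistency is real and limited in reach. The 7- and 15-day rules omit the severity and frequency test that the protocol applies both to expectedness in general and to unanticipated problems, and nothing restores it for the FDA route. Read literally, a fatal or unusually severe form of a listed reaction need not be expedited to the FDA and the manufacturer.

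That consequence rests on two assumptions: that the brochure lists broad classes like those in section IV.D, and that described is taken to mean that the term appears. The conflict between the definitions rests on neither. No estimate or efficacy conclusion is affected, and oversight by the Sponsor, the DSMC and the IRB remains in place. The text should be corrected, but participants are not left unmonitored.

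**What to change.** In both the 7-day and the 15-day sections, replace the sentence that defines an unexpected event with the test from the Expectedness section: an event is unexpected if its nature, severity or frequency is not consistent with the risk information in the named reference document. A cross-reference to that section would also serve.

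Name one reference document for the Expectedness section and both FDA rules. The present text points to a brochure in two places and to unspecified risk information in the third, while section IV.D quotes the package insert and the reference list contains product labelling. The choice could be the brochure, if one exists, or the package insert together with section IV.D.

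The change is a wording amendment in three places and needs no new data or procedures. The downside is possibly a few more expedited reports among the 50 treated patients planned.

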# 15 Calendar Day Written Report

The Sponsor will notify the appropriate review division at the FDA, in a written IND Safety Report, of any serious, unexpected AE that is considered reasonably or possibly related to the use of the investigational product. An unexpected adverse event is one that is not already described in the investigational product's investigator brochure.

Written IND Safety reports will include an Analysis of Similar Events in accordance with regulation 21 CFR § 312.32. All safety reports previously filed by the Sponsor with the IND concerning similar events will be analyzed and the significance of the new report in light of the previous, similar reports commented on.

Written IND safety reports with Analysis of Similar Events will be submitted to the appropriate review division at the FDA, and the manufacturer of the investigational product within 15 calendar days of first learning of the event, using Form FDA 3500A.

Written IND Safety Reports will be submitted to the IRB(s) of record in accordance with IRB Guidelines.

# IND Annual Reports

The Sponsor will provide annual reports to the appropriate review division at the FDA within 60 days of the IND's anniversary date, until the IND is withdrawn or terminated.

#### ii. To Safety Monitoring entity:

[name]: 18-0242 Page 13 Version: 07/03/2019

SAEs will be reported to the safety monitoring entity at the next scheduled research team meeting or as defined in the Safety Monitoring Plan, which ever applies to this study.

## 2. Unanticipated Problems

## a. Definition of Unanticipated Problems (UAP)

An unanticipated problem involving risk to participants or others includes any incident, experience, or outcome that meets **all** of the following criteria:

- Unexpected in terms of nature, severity, or frequency given (a) the research procedures
  that are described in the protocol-related documents, such as the Institutional Review
  Board (IRB)-approved research protocol and informed consent document; and (b) the
  characteristics of the participant population being studied;
- Related or possibly related to participation in the research ("possibly related" means there is a reasonable possibility that the incident, experience, or outcome may have been caused by the procedures involved in the research); and
- Suggests that the research places participants or others at a greater risk of harm (including physical, psychological, economic, or social harm) than was previously known or recognized.

# b. Unanticipated Problem Reporting

The Site Principal Investigator will report unanticipated problems (UAPs) to the reviewing Institutional Review Board (IRB) per IRB policy.

#### c. Reporting Unanticipated Problems to Participants

Any event which may relate to subjects' willingness to continue participation will be provided to the subjects, per IRB policy.

# H. Data and Safety Monitoring

The PI will be responsible for monitoring the trial, in addition to overseeing the safety and efficacy of the trial, executing the DSM plan and complying with all reporting requirements to the local and federal authorities. This oversight will be accomplished through additional oversight from the Data and Safety Monitoring Committee (DSMC) at the University of Colorado Cancer Center (CU Cancer Center).

The DSMC is responsible for ensuring data quality and patient safety for all clinical studies at the CU Cancer Center. A summary of the DSMC's activities is as follows:

- · Conduct internal audits
- Ongoing review of all serious adverse events (SAEs), unanticipated problems (UAPs) and reportable adverse events (AEs)
- Has the authority to close and/or suspend trials for safety or trial conduct issues
- May submit recommendations for corrective actions to the CU Cancer Center's Executive Committee

All SAEs, UAPs and reportable AEs are to be reported to the DSMC within 5 business days of receiving notification of the occurrence.

[name]: 18-0242 Page 14 Version: 07/03/2019

The PI will provide a DSM report to the CU Cancer Center DSMC on a 6-month basis. The DSM report will include a protocol summary; current numbers; summary of toxicity data to include specific SAEs, UAPs and AEs; any dose modifications; all protocol deviations; and protocol amendments. Results and recommendations from the review of this 6-month report by the DSMC will then be submitted by CHCO to COMIRB at continuing review.

Study audits conducted by the DSMC will consist of a review of the regulatory documents, consent forms, and source data verification. Documentation of the audit conducted by the DSMC will then need to be submitted to the IRB of record at the time of the IRB's continuing review of this trial.

Importantly, the DSMC is composed of personnel that includes persons with specialty training in pediatric oncology and pediatric surgery. The DSMC at our institution routinely monitors both adult and pediatric trails at our institution. The oversight of our study will include normal DSMC activities with an additional specific review of our study after the first phase of enrollment to evaluate the safety of our study. DSMC approval will be obtained prior to proceeding to the second enrollment phase of enrollment.

# **Study Stopping Criteria**

The objective of the safety review is to decide whether the study should continue per protocol, proceed with caution, be further investigated, be discontinued, or be modified and then proceed. Suspension of enrollment is a potential outcome of the safety review.

This study may be temporarily suspended or prematurely terminated if there is sufficient reasonable cause. Written notification, documenting the reason for study suspension or termination, will be provided by the suspending or terminating party (DSMC) to the PI, funding agency, and regulatory authorities. If the study is prematurely terminated or suspended, the PI will promptly inform the IRB and will provide the reason(s) for the termination or suspension.

Circumstances that may warrant termination or suspension include, but are not limited to:

- Determination of unexpected, significant, or unacceptable risk to participants defined by reporting of AEs, SAEs and UAPs
- Insufficient compliance to protocol requirements
- Data that are not sufficiently complete and/or evaluable
- Determination of futility
- Study closure based on PI decision or sponsor/funder decision

The study may resume once concerns about safety, protocol compliance, data quality are addressed and satisfy the sponsor, IRB and/or FDA.

